4.4.2 Data Collection and Follow-up for Withdrawn Subjects

Once a patient has been withdrawn from the study s/he will not be contacted by the research staff to conduct further assessments; however, survival data will be collected until one year after enrollment.

5 Study Device

5.1 A. Description of India ink

India ink (also called 'Chinese ink') is composed of *carbon particles* (black pigments traditionally produced from charring organic materials such as wood or bone and more recently from petroleum products) combined with a suspending agent (usually water) to form a liquid. The carbon particles used in India inks are usually in the form of a powder mainly comprised of amorphous particles of carbon (Bäumler 2015). The India ink used for this study, Carlo Erba ink consists of carbon particles from a well-defined charcoal. The SOP with specifics of this ink and its preparation, also developed by [name]' lab and the same pharmacy in Brussels, is attached (SOP 63.2). The company that makes the charcoal preparation (Carlo Erba, headquartered in Milan, Italy; manufacturer =Carlo Erba Reagents, [name]) maintains a website with details of the contents of its charcoal products and its safety data sheets, <https://www.carloerbareagents.com/en/catalog/product/view/id/420433/category/28637>.

To be used in EPR oximetry, the carbon particles in ink need to have a detectable EPR signal that is affected by the presence of molecular oxygen in a quantitative and sensitive manner. Due to the amorphous 3-dimensional structure of carbon, not all inks made with suspended carbon particles have a sufficiently narrow EPR line-width to be usually used for EPR detection of hypoxia. [name]' laboratory (cf., Charlier et al. 2004, Jordan et al. 1998, and [name] 2003) has conducted a series of experiments to test the EPR signal of various formulations of India ink that they manufactured from known samples and following pharmaceutical standards appropriate for *in vivo* human use. They determined that inks made from Printex-U and Carlo Erba have the necessary characteristics to be useful for EPR.

The FDA and its counterparts worldwide have opted not to regulate the manufacture of India inks used in cosmetic tattoos or for medical uses in marking, in large part because it has a very long established history as a safe product to use in humans. Instead they have agreed to brand name marketing of inks used for marking, based on the 'predicate' of India ink being used in humans well before May 28, 1976, the enactment date of the Medical Device Amendments, or to devices that have been reclassified in accordance with the provisions of the Federal Food, Drug, and Cosmetic Act that do not require approval of a premarket approval application.

India ink (Carlo Erba ink) is not a treatment per se. It is a paramagnetic material whose properties when queried by EPR provide an assessment of the oxygen level in tissues. It is inert and stable and permanent and so, after the initial injection and response to a foreign object in the body (i.e., akin to tattoo response described above) it permits noninvasive *in vivo* measurements using EPR spectroscopy. Approximately 50micL of sterile India ink, will be injected into the distal fourth dorsal interosseous toe web.

Dartmouth's inks to be used for EPR oximetry (prepared with certifications and under SOPs meeting both US and EU/Belgian Pharmacopia Standards)			
Printex-U India ink	Carbon black (Channel Type Black Printex U Degussa AG - D 60287 Frankfurt Germany)	Carboxymethylcellulose sodium salt (CMC-Na), ultra-low viscosity Saline water (water plus .9 NaCl), medical grade	SOP used at Dartmouth was developed and tested by [name]'s CUL Laboratory and the associated hospital pharmacy Brussels, Belgium
Carlo Erba India ink	Charcoal, vegetable powder	Saline water (water plus .9NaCl), medical grade	SOP used at Dartmouth was developed and tested

	(certified as pure); Carlo Erba Reagents in France CAS 7440-44-0 product code 332658; pyrogenated	Gum Arabic, medical grade	by [name]'s CUL Laboratory and the associated hospital pharmacy Brussels, Belgium
--	--	---------------------------	--

5.1 B. Description of Nerve Conduction Study and Regimen

Electrophysiologic assessment is performed by completing a nerve conduction study (NCS). Nerve conductions are obtained using surface electrodes placed on the skin and provide a measurement of the speed of conduction of an electrical impulse through a nerve. Changes in NCS reflect axonal loss and/or damage to myelin. To perform the test, surface electrodes are placed on the skin of the distal extremity. The underlying nerve is stimulated with a very mild electrical impulse. This results in an evoked response that is recorded from a distal surface electrode. This is repeated for each nerve being tested. The response evoked by stimulation of the peripheral nerve is analyzed for morphology, speed of response and amplitude.

5.1 C. Description of SUDOSCAN

The Impeto Medical SUDOSCAN is a galvanic skin response measurement device that measures the concentration of chloride ions produced by sweat gland activity. Patients place their hands and feet on the SUDOSCAN's stainless steel plates. A low-voltage current is applied to the feet through the plate's sensor electrodes, which stimulates sweat glands to produce chloride ions. The entire scan takes between two-three minutes to complete. It is non-invasive and painless. SUDOSCAN has been cleared by the FDA since 2010 and is routinely used in clinical settings to evaluate neuropathies.

1 Image of SUDOSCAN device.

5.2 Method for Assigning Subjects to Treatment Groups

Subjects will not be randomized into treatment groups. All participants will receive EPR oximetry, clinical evaluation, and electrophysiologic testing.

5.3 Subject Compliance Monitoring

Patients must complete their baseline assessment prior to starting chemotherapy. The study staff will strive to complete EPR oximetry, electrophysiologic testing, and clinical evaluation during a single visit after the patient enrolls in the study. Testing may be separated into distinct visits if scheduling conflicts arise or per patient preference. Patients' chemotherapy progress will be monitored in the electronic medical record so that follow up visits can be scheduled during and after completion of chemotherapy. Aside from attending and completing the scheduled study visits, patients will have no further compliance requirements.

5.4 Protocol for Preparation, Administration and Maintenance of Carlo Erba ink

5.4.1 Storage (Carlo Erba India Ink)

The India ink capsules will be stored at room temperature, in sterile packaging. As available, the ink capsules are stored on a continuously rolling platform located in the study treatment room for oximetry measurements. A complete sterile kit containing all necessary items for the injection is stored in the cabinet space in the same room and clearly marked. The vortexer that is to be used immediately prior to injecting a subject is located in the same area as is a camera top record injection sites.

5.4.2 Preparation and Administration of Study Device (Carlo Erba Ink)

This study will follow the EPR Center's standard protocol for the preparation and dispensing of India ink. For detailed instructions on the preparation of Carlo Erba ink, please see *EPR Center's Standard Method 63.2, "SOP for Preparation of Carlo Erba Ink: For injection in Humans"*. Briefly, the materials used are purified charcoal Carlo Erba (Cod 332658) (Depyrogenated for human use) as the pigment and saline water (NaCl 0.9%) and gum Arabic ²(USP quality) for the aqueous suspension. Briefly, the methods can be described as: First create a solution of gum Arabic and saline water. Then add the charcoal pigment, then distribute into vials, place in an ultrasonic bath and sonicate for 30 sec. Add stopper and cap. Seal and crimp the vials and sterilize the vials at 121°C for 20 min using the "liquids" program of the autoclave. Add labels to each individual vial with pertinent information about the date, use, batch, expiration date, etc.

The methods and materials for making Carlo Erba ink were developed and tested in Brussels under the supervision of the Project 1 PI for the NCI grant, [name]. These methods and tests have been published (see Jordan et al 1998) and the materials used have already been used for more than 20 years in St- Luc Hospital for preoperative marking (about 200 patients/year). Charcoal particles (Carlo Erba, Codex, diameter 3 to 10 micrometer) will be suspended (agitation and sonication) using a suspending agent (3% Arabic gum in saline) approved for clinical use of parenteral injection. Endotoxins will be removed by dry heating of the charcoals (2 hours at 220° C). Sterilization procedure will be carried out by using moist heat in an autoclave at 121°C for 20 min. The batches will be prepared in single use 1mL serum bottles with rubber stoppers to facilitate the injection procedure. Materials will be released for human use after regular quality control tests (sterility) are carried out.

The administration (injection) of the ink is detailed in SOP 71.2 (attached). Only designated clinicians who have completed standard in-person training by an experienced physician injector will be allowed to perform the ink injections. Briefly, these are the steps: in advance of injecting the ink, the study team should have in place two vials of India ink, the kit for injection, a camera, data collection forms, and the vortexer. Then, for a consented subject, the study physician doing the injection should first prepare the site (written here for skin) using 70% alcohol or other appropriate skin preparation such as betadine or other preparative skin cleanser. To inject the ink, first vigorously shake/mix the ink vial, preferably with a vortex mixer, for at least 5 minutes prior to drawing up ink into syringe. Continue to shake and warm bottle of ink by hand until ready to ready to inject. Draw up about 50µl of ink into a 0.5 ml insulin or tuberculin syringe with an attached 29g ½ in needle immediately before injection. Wipe the needle with an alcohol wipe to

1.1 ² From the e-CRF code, current as of August 11, 2016: Listing of ingredients generally recognized as safe in Title 21 of the FDA: §582.7330 Gum Arabic. (a) Product. Acacia (gum arabic). (b) Conditions of use. This substance is generally recognized as safe when used in accordance with good manufacturing or feeding practice.

remove excess ink before injecting into patient. Place needle at 20-30 degrees to the skin and inject between 2 to 5 units using the syringe units, which corresponds to ~20-50 μ l at depth of ~5mm from skin surface. Allow the pressure to stabilize for a few seconds and then, while withdrawing the needle, pull back on plunger to minimize ink release in needle track. Then remove needle and dispose safely. Clean the injection site of ink using fresh skin cleaner. Mark sites with non-permanent ink and photograph site. Offer a band-aid. Record pertinent information on the data recording form.

5.4.3 Dispensing of Study Device (Carlo Erba ink)

Regular device reconciliation checks will be performed. Information tracked will include which device was injected in a given subject; which device container(s) was opened; whether the subject actually received the assigned device; and which device(s) was inadvertently damaged in handling/dispensing and therefore not to be used for human subjects. This reconciliation will be logged on the device reconciliation form, and signed and dated by the study team members who are designated to perform this task.

5.4.4 Return or Destruction of Study Device (ink)

At the completion of the study, there will be a final reconciliation of the vials of ink that were shipped, vials consumed, and vials remaining. This reconciliation will be logged on the device reconciliation form, signed and dated. Any discrepancies noted will be investigated, resolved, and documented prior to return or destruction of unused study device. Vials destroyed on site will be documented in the study files.

6 Study Procedures

6.1 Schedule of Assessments

	Visit 1 (prior to beginning chemotherapy)	Visit 2 (mid-point of chemotherapy treatment or at onset of CIPN symptoms)	Visit 3 (one week or more after completion of chemotherapy)	Unscheduled EPR oximetry readings	Blood Draw Visits
Informed Consent	X				
Inclusion/Exclusion Criteria	X				
Neurological Exam	X	X	X		
Neurologic History	X				
Ink Injection	X				
Nerve Conduction Study	X	X	X		
Sudoscan	X	X	X		
EPR Oximetry Reading	X ¹	X ²	X ²	X	
Total Neuropathy Score	X	X	X		

Toronto Clinical Neuropathy Scoring System	X	X	X		
National Common Institute – Common Toxicity Criteria V.3	X	X	X		
Questionnaires- - McGill pain - Survey of Autonomic Symptoms - Subset of NQoL-DN - NTSS-6	X	X	X		
Blood Draw for Genetic Testing					X ³
Blood Draws for NF-L Assay					X ⁴

1. As many as 5 EPR measurements may be performed prior to beginning chemotherapy.
2. As many as 5 EPR measurements may be performed in the ±18 days surrounding the electrophysiologic assessments.
3. Blood for genetic testing can be drawn at any time during study participation.
4. Blood for NF-L testing will be drawn prior to the beginning of chemotherapy, prior to each scheduled chemotherapy treatment, and after the completion of chemotherapy.

6.2 Visit 1

Before beginning chemotherapy, and after providing informed consent, patients will receive an injection of India ink. Patients will then be scheduled to meet with a designated investigator for clinical assessments, which will occur prior to the start of chemotherapy. The neurologic assessment will include a standard neurologic history, neuropathy symptom questionnaire (NTSS-6 [Bastyr et al., 2005]), portions of the Total Neuropathy Score (TNS [Cornblath et al., 1999]), the National Common Institute – Common Toxicity Criteria V.3 (NCI-CTCv3), Toronto Clinical Neuropathy Scoring System, McGill pain questionnaire (Melzack, 1975), Survey of Autonomic Symptoms questionnaire, and a subset of a neuropathy-specific quality of life instrument (NQoL-DN, [Vinik et al., 2005]). As part of the neurologic examination, strength, sensation, and reflexes will be tested. Sensation testing may include pin, temperature, and vibration assessments using a Rydel-Seiffert tuning fork. Specific tests conducted will be at the discretion of the study neurologist. Assessments will be performed by one of the study neurologists.

Subjects will also receive their baseline electrophysiological assessment at this visit. See section 1.2.1 for device information. Sensory conductions may include sural, medial plantar and dorsal sural antidromic testing with assessment of peak to peak amplitudes of sensory nerve action potentials and sensory conductions. Motor conductions may also be tested in tibial and peroneal nerves with measurement of baseline to peak amplitude of the compound muscle action potential, motor conduction velocities, and distal motor latencies. Recording will be performed from the extensor digitorum brevis and tibialis anterior muscles. Additional or different nerves may be tested at the discretion of the examiner. Temperature will be controlled and data compared with normative age-matched reference data. Testing will be performed by EMG technicians trained in

performing electrodiagnostic studies or the study neurologist. Testing will be repeated for each nerve to ensure verifiable amplitudes. The SUDOSCAN recordings will be made with both the patients' hands and feet.

Subjects will report to the Department of Radiation Oncology at Dartmouth-Hitchcock Medical Center for EPR oximetry. The EPR Center's established procedures for the injection of India ink will be followed. Subjects will receive an injection of ink in the foot over the distal fourth dorsal interosseous toe web. Subjects may require 2 or more days after the injection in order for the ink to settle before the first EPR oximetry measurement can be performed. As many as five measurements will be performed prior to beginning chemotherapy.

The standard oximetry measurement procedure consists of acquiring continuous EPR scans to characterize 1) baseline tissue oxygen levels 2) tissue oxygen levels in response to inhalation of enriched oxygen mixture and 3) response to oxygen levels in tissue to discontinued breathing of enriched oxygen. The total time for one measurement is approximately 30 minutes: approximately 10 minutes while breathing room air, then ~10 minutes while breathing enriched oxygen by non rebreather face mask, followed by ~10 minutes while resuming breathing room air.

6.3 Visit 2

Visit 2 will be scheduled at the onset of CIPN symptoms or at the mid-point of chemotherapy treatment. If a patient reports symptoms of CIPN to their nurse or physician, or if the patient's provider suspects CIPN is present prior to midpoint of therapy, the subject will be scheduled for Visit 2, in which the electrophysiologic and clinical assessments are standard of care. For patients who do not show signs of CIPN by the mid-point of their treatment, the study staff will coordinate a visit for clinical and electrophysiological assessment. These assessments will be identical to the tests conducted at Visit 1.

Patients will also return to the Department of Radiation Oncology for their second round of EPR measurements. The continuous EPR will take approximately 30 minutes (~10 minutes breathing room air, ~10 minutes of enriched oxygen, ~10 minutes breathing room air again). As many as five measurements will be made in the ± 18 days surrounding the electrophysiologic assessments at Visit 2.

6.4 Visit 3

Visit 3 will take place no sooner than one week after the completion of chemotherapy. The procedures for this visit will be the same as Visits 1 and 2: patients will receive clinical and electrophysiological assessments, and EPR oximetry measurement. As many as five measurements will be made in the ± 18 days surrounding the electrophysiologic assessments at Visit 3.

6.5 *Unscheduled EPR Oximetry Readings*

Subjects who develop symptoms of CIPN may experience fluctuations of these symptoms. Unscheduled EPR oximetry measurements may be conducted if a subject experiences change in these symptoms as the PI sees as appropriate.

6.6 *Blood Draws for Serum Biomarker Assessment*

Prior to the start of chemotherapy, prior to each scheduled chemotherapy treatment, and after the completion of chemotherapy, patients will provide a blood sample (2 tablespoons) for

measurement of NFL. All attempts will be made by the study team to obtain the blood sample at the time of the patient's clinical blood draw prior to chemotherapy. In the event that this is not feasible, the patient will have the option of having a separate blood draw done for study purposes. A tube will be filled and labelled with the subject ID #, the study name, and date of draw. The tube will be processed and stored in a -80 degree freezer until they are shipped for analysis. Samples will be batched for shipment. A lab requisition form will be included in the shipment. Stored samples will not have patient information on the label.

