4.4 Early Withdrawal of Subjects

4.4.1 When and How to Withdraw Subjects

Subjects will be withdrawn from the study if they are no longer able or willing to participate. If a participant is unable to continue with the study procedures or is deemed lost to follow up, the PI or designee will mail a signed letter to the patient to inform them of their withdrawal from the study. Subjects will be deemed lost to follow up if they fail to present for ongoing cycles of chemotherapy. If a subject declines additional cycles of chemotherapy or cannot complete the planned number of cycles, they will not be withdrawn, but a post chemo-therapy assessment will be performed. Subjects will be withdrawn if they develop an impairment that would interfere with clinical and electrophysiologic assessment.

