7.1 Sample Size Determination

This pilot study is designed for proof of concept and to establish the bedrock for a future trial with a more robust sample. The secondary objective of this pilot is to demonstrate effective recruitment, screening, assessment processes, and high participant retention. We will assess the proportion of potential participants that: meet inclusion criteria, consent to participate, and complete all assessments.

Thirty (30) patients will be enrolled in the study, and it has been estimated that ten (10) patients will develop CIPN during their taxane treatment. Accurate incidence of CIPN varies significantly; the average incidence is 70% (Seretny et al., 2014), with ranges from 30% to 90%. A conservative estimate is that 30%-50% of patients in this trial will develop symptoms of neuropathy during their chemotherapy treatment. Development of CIPN will be determined based on the results of their neurologic assessments. For data analysis, the patients will be divided by this CIPN status into two groups. Primary endpoints are continuous metrics: Endpoint 1) neurological phenotyping involves electrophysiological assessment (e.g. nerve conduction, EMG readings, SUDOSCAN results), and Endpoint 2) tissue oximetry involves the EPR measures). The mean levels of each electrophysiological or oximetry metric will be assessed between the two groups of patients (with CIPN vs. without) over time (at timepoints: before, mid-, and post-chemotherapy) using repeated measures ANOVA. This method will also assess the within-subject changes in the electrophysiological and EPR oximetry metrics over time, from baseline through post-chemotherapy, as well as the interaction between CIPN status and time. With 15 patients per group, we anticipate that we will have 80% power to detect a between-groups difference in longitudinal EPR oximetry measures by CIPN status of 28%, assuming a correlation of 0.5 among repeated measures, a standard deviation of 25%, alpha=0.05. The within-subjects and interaction tests are estimated to be able to detect an 8.5% change over time, with these same parameters (calculated using G*Power 3.1.9.2).

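### The ±18-day EPR window lets readings taken before chemotherapy ends count as post-chemotherapy, and in patients who stop early it overlaps the Visit 2 window

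*Combined protocol and SAP*

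**What the plan says.** Five provisions bear on this.

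- **EPR window.** Section 6.1, footnote 2, covers Visits 2 and 3: "As many as 5 EPR measurements may be performed in the ±18 days surrounding the electrophysiologic assessments". Sections 6.3 and 6.4 repeat it for each visit: "As many as five measurements will be made in the ± 18 days surrounding the electrophysiologic assessments at Visit 2" and "As many as five measurements will be made in the ± 18 days surrounding the electrophysiologic assessments at Visit 3".
- **Timing of Visit 2.** Section 6.3: "Visit 2 will be scheduled at the onset of CIPN symptoms or at the mid-point of chemotherapy treatment". The symptom trigger applies before the mid-point: "if the patient's provider suspects CIPN is present prior to midpoint of therapy, the subject will be scheduled for Visit 2".
- **Timing of Visit 3.** Section 6.4: "Visit 3 will take place no sooner than one week after the completion of chemotherapy". The column heading in 6.1 agrees, and 6.4 lists EPR oximetry among the procedures of that visit. No latest date is set.
- **Early stoppers.** Under 4.4.1, patients who decline further cycles or "cannot complete the planned number of cycles, they will not be withdrawn, but a post chemo-therapy assessment will be performed".
- **Analysis.** Section 7.1 compares the CIPN groups over time ("at timepoints: before, mid-, and post-chemotherapy) using repeated measures ANOVA") and also tests within-subject change and the interaction of CIPN status with time. Section 3.2 makes the longitudinal EPR difference by CIPN status the primary endpoint.

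The documents set no minimum gap between Visits 2 and 3. They do not require that Visit 3 EPR readings follow the end of chemotherapy, and they do not assign a reading to a timepoint by date. Section 6.5 adds unscheduled readings for patients whose symptoms change, without saying whether one that falls inside a visit window counts towards that visit.

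**The concern.** The analysis needs three separate states: before, during and after chemotherapy. The window is centred on the electrophysiologic assessment and reaches back 18 days, but the visit itself may fall only 7 days after treatment ends. Followed literally, the window admits on-treatment readings to the post level. This can happen in either CIPN group.

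The second problem is tied to CIPN status. A Visit 2 brought forward by symptoms exists only for symptomatic patients. The background section describes CIPN as dose-limiting, and 4.4.1 provides for patients who do not finish, so a patient whose symptoms trigger Visit 2 and who then has no further cycles is foreseeable. In that patient the mid and post sets of readings can come from the same calendar days. Their difference then says little about change from mid-treatment to after treatment, even if each reading is used only once. Section 7.1 expects about ten CIPN patients, so a few such cases would carry weight in the mid-to-post change and the CIPN-by-time test. Section 7.1 also uses the pre- and mid-chemotherapy values to choose metrics for future study.

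**Working it through.** The documents state no overlap figure, so there is none to reproduce. The check is interval arithmetic.

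**Inputs.** Half-width of the window: 18 days (6.1 footnote 2, 6.3, 6.4). Earliest Visit 3: day 7, with day 0 the completion of chemotherapy (6.4). Let t2 and t3 be the days of the Visit 2 and Visit 3 electrophysiologic assessments.

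**1. Days before completion that count as post-chemotherapy (any patient).** The Visit 3 window opens on day t3 - 18, so the exposed period is max(0, 18 - t3) days.
- t3 = 7: window from day -11 to day +25, so 11 days fall before completion.
- t3 = 14: 4 days.
- t3 = 18 or later: none.

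**2. Overlap of the Visit 2 and Visit 3 windows.** The windows are [t2 - 18, t2 + 18] and [t3 - 18, t3 + 18]. The overlap is max(0, 36 - (t3 - t2)) days.

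With t2 = 0 and t3 = 7 the windows are day -18 to +18 and day -11 to +25. They share day -11 to day +18: 36 - 7 = 29 days.

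The text can be read three ways: literally, with Visit 3 readings required to follow completion (day 0 on), or with Visit 3 readings required to be at least 7 days after it (day 7 on). With Visit 3 on day 7:

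| Visit 2 on day | Literal | From day 0 | From day 7 |
|---|---|---|---|
| +5 (after last dose) | 34 | 23 | 16 |
| 0 | 29 | 18 | 11 |
| -7 | 22 | 11 | 4 |
| -14 | 15 | 4 | 0 |
| -21 | 8 | 0 | 0 |
| -29 | 0 | 0 | 0 |

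Holding Visit 2 on day 0 and moving Visit 3 later, the literal overlap is 22 days at day 14, 15 at day 21, 8 at day 28 and 0 at day 36.

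Twenty-nine days is therefore not a ceiling. If completion means the last dose and Visit 2 comes after it, the overlap approaches 36 days.

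**3. Patients who complete the course.** With Visit 2 at the mid-point and Visit 3 on day 7, the windows overlap only if the mid-point is less than 36 - 7 = 29 days before completion. The documents give no regimen length, so this cannot be settled. The pre-completion exposure in step 1 applies to these patients regardless.

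**4. Number affected.** The documents give no early-stopping rate, so no count or size of bias follows.

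**The case against.** The strongest reply is that overlapping permitted dates are not shared readings. The Study Summary describes three distinct time points with up to five measurements for each. Aim 1 in Section 2 speaks of five measurements within each visit window, and 6.3 calls the Visit 2 readings a second round. The natural reading is a separate set for each visit, labelled by visit. This stands. A reader might infer that the same reading is averaged into both timepoints, so that with s of 5 readings shared the mid-to-post change shrinks to 1 - s/5 of its size. Nothing in the documents says readings are used twice, how many would be shared, or even that the up to five readings are averaged.

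It can also be said that a reading near symptom onset is a proper Visit 2 reading even if treatment has just stopped, because Visit 2 is defined by onset or mid-point. This stands too, and Aim 3 wants those readings. Likewise, one week is only the earliest date for Visit 3, and staff may schedule it later.

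Finally, 7.1 powers the between-groups test separately from the within-subject and interaction tests. A reader might infer that the between-groups result is biased by a known amount. The arithmetic does not show that, since an effect averaged over time is less exposed than a mid-to-post change.

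None of this removes the conflict within the Visit 3 rules. Labelling by visit does not stop a Visit 3 reading from preceding the end of chemotherapy, nor the two sets from covering the same dates.

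**Conclusion.** The point holds as a conflict between stated rules that reaches the primary longitudinal analysis. On the literal text, a post-chemotherapy EPR reading may precede the end of chemotherapy by up to 11 days, in any patient whose Visit 3 is on day 7. In a patient whose symptoms trigger Visit 2 and who stops on that day, the Visit 2 and Visit 3 windows overlap on every reading of the text when Visit 3 is on day 7: 29, 18 or 11 days, and more if Visit 2 follows the last dose. The overlap shrinks as the visits move apart, and on the literal text it is gone at 36 days.

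The likely consequence is a blurred mid-to-post contrast and CIPN-by-time interaction, mainly in the CIPN group. This assumes that some CIPN patients do stop near symptom onset and that their readings fall in the overlapping dates. The frequency and the size of the effect cannot be computed from the documents. Double counting is possible but not shown.

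**What to change.** Add to footnote 2 of 6.1 and to 6.3 and 6.4:

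- Visit 3 EPR readings are taken only after completion of chemotherapy, defined for patients who stop early as the last dose received. Reconcile this with the one-week rule in 6.4 by stating whether that rule binds each EPR reading or only the visit assessment.
- Each EPR reading, including an unscheduled one under 6.5, is assigned to one visit only.
- Readings prompted by symptom onset remain Visit 2 readings even if chemotherapy has just stopped.

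In 7.1, flag early stoppers and add a sensitivity analysis that leaves them out.

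The date limit removes the pre-completion readings. It does not by itself separate the windows: in the day 0 and day 7 case, 18 or 11 days remain open to both visits. The single label and the sensitivity analysis are therefore needed as well.

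Do not recode the mid timepoint as not applicable in early stoppers. Section 7.1 names repeated measures ANOVA with no missing-data method, and the conventional form drops incomplete cases. Recoding could remove early-stopping CIPN patients altogether and discard valid onset readings.

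The cost is a few sentences, a date check in the database and one extra analysis. With Visit 3 on day 7, its EPR window narrows from 36 days to 25 (day 0 to 25), or to 18 (day 7 to 25) if the one-week rule binds each reading. A few patients may have fewer readings.
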